12.2 Adjustment for Covariates

Not applicable.

12.3 Handling of Missing Data

Missing data imputation rules are described in [Section 5.2](#).

12.4 Multiple Comparisons / Multiplicity

No hypothesis testing is planned.

12.5 Examination of Subgroups

Subgroup analysis by *MECP2* mutation groupings may be performed for RSBQ and CGI-I.

12.5.1 *MECP2* Mutation Groupings

The number and percentage of subjects will be examined in the following *MECP2* mutation groupings.

| Mutations | Code in EDC | Category | Severity |
|---------------|-------------|------------------------|------------------|
| R106W | 1 | R106W | Severe |
| R133C | 2 | R133C | Mild |
| T158M | 3 | T158M | Moderate |
| R168X | 4 | R168X | Severe |
| R255X | 5 | R255X | Severe |
| R270X | 6 | R270X | Severe |
| R294X | 7 | R294X | Mild |
| R306C | 8 | R306C | Mild |
| C298G (L100V) | 9 | Other mutations | Mild |
| G317A (R106Q) | 10 | Other mutations | Mild |
| C421G (Y141X) | 11 | Other mutations | Unknown |
| C455G (P152R) | 12 | Other mutations | Severe |
| C302G (P101R) | 13 | Other mutations | Severe |
| C401G (S134C) | 14 | Other mutations | Severe |
| C423G (Y141X) | 15 | Other mutations | Unknown |
| C468G (D156E) | 16 | Other mutations | Mild |
| C674G (P225R) | 17 | Other mutations | Mild |
| C965T (P322L) | 18 | Other mutations | Mild |
| 710del1 | 19 | Other mutations | Severe |
| 806del1 | 20 | Other mutations | Severe |
| 807del1 | 21 | Other mutations | Severe |
| 1157del41 | 22 | C-terminal Truncations | Mild |
| 1157del44 | 23 | C-terminal Truncations | Mild |
| 1163del26 | 24 | C-terminal Truncations | Mild |
| 1163del35 | 25 | C-terminal Truncations | Mild |
| 1164del44 | 26 | C-terminal Truncations | Mild |
| 1168del6 | 27 | C-terminal Truncations | Mild |
| Exon 1+2 | 28 | Large Deletions | Severe |
| Exon 3 | 29 | Large Deletions | Severe |
| Exon 3+4 | 30 | Large Deletions | Severe |
| Exon 4 | 31 | Large Deletions | Severe |
| Exons 1-4 | 32 | Large Deletions | Severe |
| All Others | 33 | Other mutations | Derived from CRF |

Missing and unknown severity will not be imputed.

13. METHODS OF EFFICACY ANALYSES

13.1 Analysis of Continuous Efficacy Endpoints

Descriptive statistics for all efficacy endpoints listed in [Section 12.1](#) will be tabulated by treatment group of the antecedent study. The summaries of the change from baseline results will be presented in two ways (main analysis and exploratory analysis) as specified in [Section 5.1](#).

14. SAFETY ANALYSES

All safety analyses will be performed using the Safety Analysis Set. Safety summaries will be summarized using descriptive statistics by treatment group of the antecedent study and overall. For each continuous measure in clinical laboratory variables, vital signs, and electrocardiogram, change from baseline results will be presented in two ways as specified in [Section 5.1](#).

The primary safety endpoints are:

- Treatment-emergent adverse events (TEAEs)
- Serious adverse events (SAEs)
- Withdrawals due to adverse events (AEs)
- Potentially clinically important changes in other safety assessments

14.1 Adverse Events

Adverse events will be coded using MedDRA dictionary, Version 23.0 or newer.

An AE (classified by preferred term) will be considered a treatment-emergent AE (TEAE) if started after first dose administration and no later than last dose date + 30 days. AEs reported on Day 1 based on Baseline (pre-dose) findings (e.g., clinically significantly abnormal vital signs, laboratory test results, or electrocardiogram parameters) will not be considered as TEAEs.

The event counts, the number, and percentage of subjects reporting TEAEs in the treatment group of the antecedent study and overall will be tabulated by system organ class (SOC) and preferred term; by SOC, preferred term, and maximum severity; and by SOC, preferred term, and relationship to study drug. If more than one TEAE occurs with the same preferred term for the same subject, then the subject will be counted only once for that preferred term using the most severe and most related occurrence for the summarization by severity and by relationship to study drug. The display in these tables will be sorted alphabetically by SOC and then by descending subject frequency for the preferred terms (combined counts from overall group) within each SOC.

The event counts, the number and percentage of subjects with any TEAEs will also be tabulated by preferred term without SOCs. This table will be sorted by descending subject frequency.

The incidence of most frequently reported (preferred terms reported by $\geq 5\%$ of subjects overall) TEAEs, SAEs reported after treatment start, TEAEs leading to drug withdrawn, and TEAEs related to study drug will be summarized by SOC and preferred term. The tables will be sorted alphabetically by SOC and then by descending frequency within each SOC in overall group. In addition, the incidence of fatal treatment-emergent AEs (i.e., events that cause death) will be summarized separately by SOC and preferred term.

These summary tables except for the most frequently reported TEAEs tables will also be presented by relationship to COVID-19 Infection (Not related to COVID-19 Infection vs. Related to COVID-19 Infection).

An AE listing by subject will display all events, including those which are not treatment-emergent, and will include the verbatim term in addition to the MedDRA SOC and preferred term. This listing will also include all relevant eCRF data associated with the event: date of onset, date resolved, date of last dose, severity, frequency, outcome, relationship to study drug, and action taken with study drug. Separate listings will be presented for subjects with treatment-emergent SAEs, related TEAEs, TEAEs leading to drug withdrawn, fatal TEAEs (if any), and TEAEs Related to COVID-19 Infection.

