7.2.2.1 Duration

The start and stop dates for AEs will be recorded using the following criteria:

- **Start:** Date of the first episode of the AE or date of significant sustained worsening in severity
- **Stop:** Date when AE either ceased permanently or changed in severity

For AEs of diarrhea, the start date and stop date of a decrease in severity will also be recorded.

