7.3 Time Period and Frequency for Event Assessment and Follow-Up

Adverse events with an onset before the first dose of open-label trofinetide in the present study will be recorded as an AE in the antecedent study. All ongoing AEs from Study

ACP-2566-003 will be carried over after informed consent has been obtained for the present study and recorded from Baseline for the present study until resolution or the follow-up safety assessment. An adverse event occurring after the first dose of open-label trofinetide in the present study will be recorded as an AE in the present study. Adverse events for the present study will be recorded from the time of first dose of open-label trofinetide through the safety follow-up period.

All AEs must be either resolved or stable at the end of the safety follow-up period. If ongoing at the end of the safety follow-up period, the subject should be referred for appropriate treatment.

In the event that a subject discontinues and has an ongoing AE at the time of discontinuation (Section 4.4.2) or is withdrawn from the study because of an AE, the subject should be followed and treated by the Investigator until the AE has resolved, stabilized, or a new chronic baseline has been established.

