9.5.2 Primary Analyses

Adverse events will be classified into standard terminology using the Medical Dictionary for Regulatory Activities (MedDRA). All AEs will be listed and TEAEs will be summarized by system organ class and preferred term. A TEAE is defined as an AE that started after the first administration of study drug and no later than the last administration of study drug plus 30 days. Summaries by maximum severity and by relationship to study drug will also be provided. Serious TEAEs, fatal AEs, and TEAEs leading to discontinuation will also be summarized.

Descriptive summary statistics for ECG, vital signs and weight, and clinical laboratory parameters, including observed values and changes from Baseline, will be tabulated by timepoint. Additionally, categorical analyses will be conducted on the incidence of subjects with prolonged QTc intervals and changes in QTc intervals in accordance with International Council for Harmonisation (ICH) guidelines.

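### Diarrhea carried over from Study 003 that only improves on open-label drug can be counted as a diarrhea TEAE, because TEAE status rests on start date and no rule links diarrhea severity records

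*SAP*

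**What the plan says.** Protocol 7.2.2.1 sets the dates of every AE. The start is the "Date of the first episode of the AE or date of significant sustained worsening in severity". The stop is the "Date when AE either ceased permanently or changed in severity". An improvement therefore closes an AE entry but, in general, does not open a new one. Diarrhea is the one exception: "For AEs of diarrhea, the start date and stop date of a decrease in severity will also be recorded".

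Protocol 7.3 assigns an AE with onset before the first open-label dose to the antecedent study. It also says that AEs still ongoing from Study 003 "will be carried over after informed consent has been obtained for the present study and recorded from Baseline", until they resolve or the safety follow-up takes place.

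Protocol 9.5.2 classifies by start date: "A TEAE is defined as an AE that started after the first administration of study drug". SAP 14.1 does the same: an AE "will be considered a treatment-emergent AE (TEAE) if started after first dose administration and no later than last dose date + 30 days". The SAP's only exclusion is for "AEs reported on Day 1 based on Baseline (pre-dose) findings". Neither document says how the severity stages of one diarrhea episode are linked, or what status an improving stage has.

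SAP 14.1 tabulates event counts and subject counts by antecedent treatment group and overall. A subject counts once per preferred term, at the most severe occurrence.

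**The concern.** Take a former-trofinetide subject who enters with moderate diarrhea from Study 003 that eases to mild in Week 3. If the easing is a separate record, that record starts after the first open-label dose and passes the TEAE test, although nothing new or worse has happened. The maximum-severity table would show a mild on-study event. The same course of any other AE gives no TEAE, because improvement gives it no new start date.

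TEAEs are the first primary endpoint. Protocol 1.3 shows diarrhea as the leading tolerability signal in the pediatric Phase 2 study: 56% at 200 mg/kg BID against 4% on placebo. Diarrhea ongoing at rollover is most likely in subjects coming from trofinetide, so resolving diarrhea could appear as new diarrhea under continued treatment in that column. Event counts for diarrhea would also rest on a different recording rule from those for every other preferred term.

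**Working it through.** No figure in the plan depends on this point. The sample size is not power-based and no testing is planned, so there is nothing to reproduce.

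**Step 1. Apply the stated rule to possible record layouts.** A record is a TEAE if its start is after the first dose and no later than the last dose + 30 days. In A to C, onset is 20 days before the first open-label dose and the decrease comes 10 days after it. In D, onset is 5 days after the first dose and the decrease 15 days after it.

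| Layout | TEAE records | Subject counted |
|---|---|---|
| A. Carried-over diarrhea, one record, decrease stored as an attribute | 0 | no |
| B. Carried-over diarrhea, milder stage is its own record | 1 | yes |
| C. Same carried-over course, any other AE | 0 | no |
| D. On-study diarrhea that eases once, split records | 2 | yes, once |

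By extension of D, an on-study severe-moderate-mild course gives 3 diarrhea events with split records and 1 for any other AE. Subject incidence is the same either way.

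**Step 2. Illustrate the size of B.** Extra subjects in a prior-treatment group = n × P(diarrhea in Study 003) × P(ongoing at rollover) × P(improves on open label) × (1 − P(has a diarrhea TEAE anyway)).

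Inputs:
- n = 90 per prior group: the planned total of about 180 (Protocol 9.3, SAP 3.5), with a 1:1 split assumed.
- Diarrhea in Study 003: 56% and 4%, the Phase 2 rates for 200 mg/kg BID and placebo, assumed to stand in.
- Ongoing at rollover: 10% to 50%, assumed.
- Improves on open label: 25% to 75%, assumed.
- Has a diarrhea TEAE anyway: 20% to 50%, assumed.

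Former trofinetide, 90 × 0.56 = 50.4:
- low: 50.4 × 0.10 × 0.25 × 0.50 = 0.63 subjects, 0.7 percentage points of 90
- high: 50.4 × 0.50 × 0.75 × 0.80 = 15.1 subjects, 16.8 points

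Former placebo, 90 × 0.04 = 3.6:
- low: 3.6 × 0.10 × 0.25 × 0.50 = 0.045 subjects, 0.05 points
- high: 3.6 × 0.50 × 0.75 × 0.80 = 1.08 subjects, 1.2 points

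Overall: (0.63 + 0.045)/180 = 0.4 points to (15.12 + 1.08)/180 = 9.0 points.

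A mid-range case (25% ongoing, 50% improving) gives 50.4 × 0.25 × 0.50 × (0.50 to 0.80) = 3.2 to 5.0 former-trofinetide subjects, or 3.5 to 5.6 points.

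**Step 3. Extra events from carried-over cases.** With one step down each, both groups together give 54 × 0.10 × 0.25 = 1.4 to 54 × 0.50 × 0.75 = 20.3 events. No overlap is removed here, because each improving course adds an event whether or not the subject is already counted.

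**The case against.** The strongest reply is that the central step is an inference. A reader might conclude that improving diarrhea *is* counted as treatment-emergent, but the documents do not go that far. The diarrhea sentence in Protocol 7.2.2.1 can be read as extra dates attached to one AE. The general definition of a start covers only a first episode or a sustained worsening. Protocol 7.3 ties pre-dose onset to Study 003. The TEAE rule asks when an AE started, not when a severity stage started. SAP Section 1 says the plan is to be read with the eCRFs, which are not part of these documents. All of this stands, so layout A, with no effect, remains possible.

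The text still leans toward split records. The stop rule closes an entry on any change in severity. A decrease with both a start and a stop date describes a stage with its own duration. Protocol 7.2.2.2 defines a recurrent AE by repeated episodes of equal severity, which suggests severity-specific records. The AE listing in SAP 14.1 names one onset, one resolution date and one severity, with no field for a decrease.

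A reader might also infer that on-study diarrhea incidence is inflated. It is not, because a subject counts once per preferred term, at the worst severity. Terms are ordered by subject frequency, so the extra events do not change the order either. Finally, the study is descriptive, the error would overstate harm rather than hide it, and the listings allow tracing. These points limit the consequence, but they do not settle how a primary-endpoint table is to be derived.

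**Conclusion.** The point holds in conditional form. Diarrhea carried over from Study 003 that only improves can be counted as a TEAE, because classification uses start date alone and nothing excludes or links an improving diarrhea record. Whether it would be counted depends on a record structure that neither document states.

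The size cannot be determined from the documents. It is zero under a single-record layout. Under split records and the assumptions above it is about 0.7 to 17 percentage points in the former-trofinetide column, at most about 1.2 in the former-placebo column, and 0.4 to 9 overall. Without the overlap factor the same inputs would give 50.4 × 0.10 × 0.25 = 1.3 to 50.4 × 0.50 × 0.75 = 18.9 former-trofinetide subjects (1.4 to 21 points). That range is not supportable for incidence, since a subject with a genuine new diarrhea event is counted anyway. The direction is the same throughout: upward, and mostly in the former-trofinetide column. This should be fixed before the AE dataset is finalized.

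**What to change.** Add to SAP 14.1:

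> A diarrhea record that starts because severity decreased takes the onset date of the episode it continues for TEAE classification, and is not counted as a separate event. Records that start because of a first episode or a significant sustained worsening are classified by their own start date as now. All raw records stay in the listings.

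The rule should stay this narrow. Merging all consecutive records under the earliest start date would give a carried-over event that worsens on study a pre-dose start. Requiring severity above that at the first dose would miss a severe event that eases to mild and then worsens again to moderate. The wording above keeps both as TEAEs, and it leaves other preferred terms alone.

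The cost is SAP wording and a step in the AE analysis dataset that links diarrhea records by stop and start dates. No new data are needed. The downside is that linkage may have to be inferred from dates. If the eCRF already stores decreases as attributes of one record, the text costs nothing and documents that choice.

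### The by-event table and dedicated listing of withdrawals due to adverse events cover only TEAEs, so a withdrawal caused by an event carried over from Study ACP-2566-003 with its pre-dose onset is in neither

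*SAP*

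**What the plan says.** Protocol 2.1.1 and SAP 14 both name withdrawals because of adverse events as a primary endpoint. The first item in the same list is restricted to treatment-emergent events; this item is not.

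SAP 14.1 defines treatment emergence by onset alone. An event "will be considered a treatment-emergent AE (TEAE) if started after first dose administration and no later than last dose date + 30 days". The cause-of-withdrawal table is then limited to that class: "TEAEs leading to drug withdrawn, and TEAEs related to study drug will be summarized by SOC and preferred term". The subject listings follow suit: "Separate listings will be presented for subjects with treatment-emergent SAEs, related TEAEs, TEAEs leading to drug withdrawn, fatal TEAEs (if any". Protocol 9.5.2 has the same restriction for events leading to discontinuation.

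Protocol 7.3 deals with events that straddle the two studies. Those with "onset before the first dose of open-label trofinetide in the present study will be recorded as an AE in the antecedent study". Events still ongoing at rollover "will be carried over after informed consent has been obtained for the present study and recorded from Baseline for the present study". They are therefore part of this study's data.

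Two other outputs bear on the point. SAP 6 counts early discontinuations by reason, and adverse event is one of the reasons in protocol 4.4. SAP 14.1 also plans a full listing: "An AE listing by subject will display all events, including those which are not treatment-emergent". Its fields include "date of onset, date resolved, date of last dose, severity, frequency, outcome, relationship to study drug, and action taken with study drug".

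**The concern.** The endpoint is wider than the two outputs meant to explain it. In a rollover study, events already in progress at the first open-label dose are expected. Protocol 7.3 provides for them, and protocol 5.1.3.1 expects some subjects to enter on a dose already reduced for tolerability. If one of these events persists and the subject stops drug because of it, that is a withdrawal due to an adverse event under the endpoint as worded, but its cause does not reach the table by system organ class and preferred term.

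Long-term tolerability is the primary question, and this table is where a reader looks to learn why subjects stopped. Its total can fall below the adverse-event count in disposition, and the SAP text gives no explanation for the difference.

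The omission may also be uneven between the prior-treatment columns. An event caused by trofinetide in the antecedent study can be ongoing at rollover only in a former-trofinetide subject. Former-placebo subjects can carry over events too, and the documents do not show how large any imbalance would be.

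**Working it through.** The plan gives no figure to reproduce. The check is to follow one event through the stated rules, then work out the size per case.

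**Tracing a carried-over event.** Take an event that began before the first open-label dose, has a complete onset date, is ongoing at Baseline, does not change in severity, and leads to permanent stopping of drug in this study.

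| Question | Rule | Result |
|---|---|---|
| Is it in this study's data? | Protocol 7.3 carry-over | Yes |
| Is it a TEAE? | SAP 14.1, onset after first dose | No |
| Is it in the withdrawal table by system organ class and preferred term? | SAP 14.1, TEAEs only | No |
| Is it in the dedicated withdrawal listing? | SAP 14.1, TEAEs only | No |
| Is the withdrawal in disposition? | SAP 6 with protocol 4.4 | Yes, as a count with no event term |
| Is it in the all-event listing? | SAP 14.1 | Yes, with onset and action taken |

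**Routes by which a carried-over event may still become a TEAE.**
- A significant sustained worsening has its own start date (protocol 7.2.2.1), so an event that worsens after the first dose can enter as treatment-emergent.
- For diarrhea, a decrease in severity also has a recorded start date (protocol 7.2.2.1).
- If dates are missing or incomplete and the timing is unclear, SAP 5.8 defaults to treatment-emergent. This does not reach a known pre-dose onset.
- Protocol 7.3 does not say which start date a carried-over record keeps. If the Baseline date were entered and the first dose fell on the same day, the event might be classed as a TEAE.

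The gap is what remains: events that keep a known pre-dose onset and lead to stopping without a later start date.

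**Size per omitted case.** Shortfall in tabulated incidence = 1/N. The value N = 180 is the planned maximum (protocol 9.3; SAP 3.5). The smaller totals and all prior-treatment group sizes are assumptions, because the documents do not give the split.

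- Overall column: 1/180 = 0.56 percentage points; 1/150 = 0.67; 1/120 = 0.83.
- Prior-treatment column: 1/120 = 0.83 percentage points; 1/90 = 1.11; 1/60 = 1.67.
- Disposition rate of discontinuation for adverse events: no change.

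The documents give no basis for the number of cases, so no total shortfall can be stated.

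**The case against.** The strongest reply is that nothing is lost. Disposition counts the withdrawal whatever the onset, and the all-event listing lets a reader trace each case to its event. That is correct, and it is why the point is minor. However, disposition gives no event term and SAP 6 states no split by prior treatment, while the full listing shows the case as one line among all events. Neither does the work of the by-event table.

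A second reply is that TEAE-only tables are conventional, match protocol 9.5.2, and fit the SAP's deliberate exclusion of Day 1 pre-dose findings. This shows that the two documents agree with each other. It does not make the table complete for an endpoint worded more broadly.

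A third is that the scenario is narrow. Exclusion criterion 5 screens out subjects judged unsuitable because of adverse events, and an event tolerated at rollover that later forces stopping will often have worsened and so gained a new start date. This stands as a reason to expect few cases. It does not rule them out, since the exclusion is a matter of judgment and an unchanged event that persists can still end treatment.

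A fourth concerns the serious-event wording in the same sentence, "SAEs reported after treatment start, TEAEs leading to drug withdrawn", which reads as wider than TEAEs. The phrase is undefined, the matching listing says treatment-emergent and the protocol says serious TEAEs, so it may simply be loose drafting. It is weak support, and the conclusion does not rest on it.

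Finally, table specifications sit in a separate document (SAP 1) that was not available and might add a footnote or reconciliation. That is possible, but the SAP text restricts both outputs to TEAEs and states no reconciliation.

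**Conclusion.** The concern holds as a minor incompleteness in how one primary endpoint is reported by event. Under the rules as written, a withdrawal caused by a carried-over event with a known pre-dose onset and no later start date is absent from both the withdrawal table and the dedicated listing. The overall discontinuation rate for adverse events is unaffected.

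The size is 0.56 percentage points per case at 180 subjects, and 0.83 to 1.67 points within a prior-treatment column of 120 down to 60 subjects (assumed sizes). How many cases there would be, and whether they differ by prior treatment, cannot be judged from the documents. The conclusion assumes that carried-over records keep their original onset date and that the separate table specifications do not already widen the scope.

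**What to change.** In SAP 14.1, define the table and the listing to cover every adverse event with the action *drug withdrawn* on or after the first open-label dose, whatever its onset, by system organ class, preferred term and prior treatment. Flag each event as treatment-emergent or carried over from Study ACP-2566-003, so that the TEAE subset specified in the protocol stays visible. Footnote any difference between the table's subject count and the adverse-event discontinuations in SAP 6. Enter the change in SAP 19, which now states that there are none, because protocol 9.5.2 specifies TEAEs leading to discontinuation.

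The cost is revised wording, one flag, one footnote and one SAP 19 entry. Onset date and action taken are already collected, so no new data are needed. The one drawback is that the reported by-event withdrawal incidence may rise slightly.

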Seizures are common, although not diagnostic. Commonly observed symptoms include awake breathing disruptions, scoliosis, and interest in social interaction (intense eye communication) (Neul et al. 2010; Percy et al. 2010). Gastrointestinal symptoms, including constipation and chewing and swallowing difficulties, are observed in the majority of patients with RTT (Motil et al. 2012). Sudden changes in mood, screaming and inconsolable crying are common behaviors in children and adolescents with RTT (Mount et al. 2001, 2002; Robertson et al. 2006; Cianfaglione et al. 2015). These impairments can further exacerbate

other symptoms and disrupt activities of daily living including educational, recreational and treatment opportunities (Epstein et al. 2016; Perry et al. 1991; Thompson and Iwata 2001; Lemmi et al. 2016). Autonomic manifestations, which include abnormalities in cardiac and respiratory function, as well as in peripheral circulation, are considered to be predominantly of central nervous system origin. Rett syndrome is also characterized by impaired growth affecting the brain and other organ systems.

Loss of purposeful hand use is a defining aspect of RTT during the onset of regression and at least 30% of individuals remain without any type of purposeful hand use (Downs et al. 2010). Individuals with some purposeful hand movements vary in their level of ability to reach for and grasp objects. The ability to self-feed is observed in 25-43% (Cass et al. 2003; Larsson et al. 2005; Downs et al. 2011). Poorer levels of hand function are associated with both age and severity of mobility impairment (Downs et al. 2011).

In adulthood, a late motor deterioration stage occurs, characterized by worsening dystonia, rigidity, and in some cases deterioration in the ability to walk and parkinsonian symptoms. Affected individuals have a yearly death rate between 1% and 2%, with 25% of all deaths characterized as sudden and unexpected (Kerr et al. 1997; Samaco and Neul 2011). Women with RTT can survive into their fifties and occasionally longer (Samaco and Neul 2011).

There are no medicines approved for the treatment of RTT. Treatment focuses on the management of each patient's symptoms and, even in that regard, is often unsatisfactory and has only a limited effect on functional improvement. Accordingly, the burden on families and other caregivers is very great (Palacios-Ceña et al. 2018).

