7.3.2 Serious Adverse Event Reporting

The reporting of SAEs by the Sponsor or designee to the regulatory authorities is a regulatory requirement. Each regulatory authority has established a timetable for reporting SAEs based upon established criteria.

Serious AEs must be reported within 24 hours of discovery to the Sponsor or its designee; use the appropriate form for initial and/or follow-up reporting.

At a minimum, events identified by the Sponsor to require expedited reporting as serious, unexpected, and related to study drug must be brought to the attention of the responsible institutional review board/ethics committee (IRB/EC), as per applicable regulations. These will be provided by the Sponsor after their assessment. For European Union member states, the Sponsor or its designee will provide reports of suspected unexpected serious adverse reactions (SUSARs) directly to the ECs, as required by local legislation. In all other countries, it is the Investigator's responsibility to provide these expedited reports to the responsible IRB/EC. It is also the Investigator's responsibility to notify the responsible IRB/EC regarding any new and significant safety information.

When an SAE occurs, Investigators will review all documentation related to the event and will complete the paper SAE form (for initial and/or follow-up information) and fax or email (within 24 hours of discovery) to the contact information provided on the SAE form.

Subjects will be followed through the safety follow-up period for 30 days after last dose of study drug for any SAEs and/or other reportable information until such events have resolved or the Investigator, in conjunction with the Sponsor, deems them to be chronic or stable.

In the event of any SAE (other than death), the study subject will be instructed to contact the Investigator (or designee) using the telephone number provided in the informed consent form (ICF). All subjects experiencing an SAE will be seen by the Investigator or designee as soon as is feasible following the report of the SAE.

Serious AEs occurring after the study follow-up period (i.e., 30 days after last dose of study drug) should be reported if in the judgment of the Investigator there is "a reasonable possibility" that the event may have been caused by the product.

SAEs should also be reported to the IRB/EC according to local regulations.

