19. CHANGES TO ANALYSES SPECIFIED IN PROTOCOL

No changes are made to the analyses specified in the protocol.

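### SAP 14.1 limits the fatal-event table and listing to treatment-emergent events, although the protocol promises all fatal AEs and SAP 19 declares no change

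*SAP*

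**What the plan says.** Protocol 9.5.2, and the synopsis in the same terms, states: "Serious TEAEs, fatal AEs, and TEAEs leading to discontinuation will also be summarized". The serious events and the discontinuations in that sentence are limited to TEAEs. The fatal events between them are not.

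SAP 14.1 states that "the incidence of fatal treatment-emergent AEs (i.e., events that cause death) will be summarized separately by SOC and preferred term". The separate fatal-event listing in the same section is also confined to TEAEs. An event is a TEAE "if started after first dose administration and no later than last dose date + 30 days".

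SAP 19 states: "No changes are made to the analyses specified in the protocol".

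Two protocol rules bring events outside that window into the study's records or safety reports. Under Protocol 7.3, ongoing AEs from Study 003 "will be carried over after informed consent has been obtained for the present study". Under Protocol 7.3.2, "Serious AEs occurring after the study follow-up period (i.e., 30 days after last dose of study drug) should be reported" where the investigator sees a reasonable possibility that the product was the cause.

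**The concern.** The SAP's rule for fatal events is narrower than the protocol's, in an analysis that belongs to the primary safety objective, and the SAP says nothing has changed. Followed as written, it would leave a death out of the table a reader consults first for mortality if the causal event began before the first open-label dose or more than 30 days after the last one. Few deaths are expected, so each carries weight. A late event reaches the sponsor only because someone suspects the drug, so it is one that a long-term safety report should show plainly.

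**Working it through.** No figure in the plan needs reproducing. The check compares the texts, and a short calculation gives context.

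**1. The two commitments**

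| Output | Protocol 9.5.2 and synopsis | SAP 14.1 |
|---|---|---|
| Fatal events, summary | Fatal AEs, no onset limit | Fatal TEAEs, by SOC and preferred term |
| Fatal events, separate listing | Not specified | Fatal TEAEs |
| Declared change (SAP 19) | – | None |

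**2. Route A: onset before the first open-label dose.** A carried-over Study 003 event has its onset before the window opens. Protocol 7.2.2.1 gives a significant, lasting worsening its own start date, so a carried-over event that worsens after the first dose would normally become a TEAE. Severity has three grades and ends at severe (Protocol 7.2.1), and fatal is an outcome rather than a grade (Protocol 7.2.2.5). An event already severe at rollover therefore has no higher grade to move to, and the rule does not clearly give it a new onset if it ends in death.

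**3. Route B: onset more than 30 days after the last dose.** Protocol 7.3 ends routine AE recording with the safety follow-up period. The follow-up contact may fall up to 4 days after day 30 (Table S–2). After that, Protocol 7.3.2 brings in only SAEs judged possibly caused by the product. A fatal one is outside the TEAE window by definition.

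**4. What is not affected.** An event that starts inside the window and proves fatal later is still a fatal TEAE. If dates are missing or incomplete and the order is unclear, SAP 5.8 treats the event as treatment-emergent. The gap therefore concerns events with a known onset outside the window.

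**5. Where such a death would still appear**

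- The by-subject AE listing in SAP 14.1 covers events that are not treatment-emergent and shows outcome.
- Death is a discontinuation reason in Protocol 4.4, and SAP 6 tabulates discontinuations by reason. An on-study death would ordinarily be counted there, without SOC or preferred term. A death after study end would not.
- The SAE summary in SAP 14.1 is defined by treatment start and has no stated 30-day end, so a late fatal SAE could be counted there, though not as a death.

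**6. Context: expected deaths.** Inputs are about 180 subjects (Protocol 9.3), 40 weeks = 280 days, and a yearly death rate of 1% to 2% (Protocol 1.1).

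- Person-years: 180 × 280 / 365.25 = 138.0
- At 1%: 138.0 × 0.01 = 1.38 deaths
- At 2%: 138.0 × 0.02 = 2.76 deaths

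This assumes no dropout and that the background rate applies to trial entrants. It counts all deaths, not those outside the window.

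**The case against.** The strongest reply is that this is a difference in wording with almost no practical reach.

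- **Route A is nearly empty.** The worsening rule re-dates most carried-over events. The exclusion criteria (Protocol 4.2) keep out subjects with newly developed clinically significant disease, clinically significant vital-sign abnormalities or ECG findings, or AEs that make them unsuitable. This stands as a limit on likelihood. It does not cover an admitted subject whose event was already severe.
- **Route B may lie outside the protocol's promise.** AEs of this study are recorded through the follow-up period, and Protocol 7.3.2 sets a reporting duty, not a commitment to tabulate. This stands in part, and Route A is the clearer departure. Still, neither document excludes late reported deaths from the fatal AEs of 9.5.2.
- **The deaths are visible elsewhere.** This also stands. A reader might infer that such a death would appear as a death in no summary at all. The disposition table and the all-AE listing do not support that reading.

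A reader might also infer that the protocol left fatal events unrestricted on purpose. Neither document gives a reason, and the sentence sits in a paragraph built on the TEAE definition, so loose drafting is equally possible. The point needs only that the two texts differ.

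**Conclusion.** The discrepancy is real and undeclared: the protocol promises fatal AEs, the SAP delivers fatal TEAEs, and SAP 19 reports no change. The consequence is limited to the SOC and preferred-term table of fatal events and its dedicated listing. Both routes to an omission are narrow, and the documents give no basis for estimating how often either would occur.

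A reader might go further and say that mortality would be understated by about a third to three quarters, since one death is 1/2.76 = 36% to 1/1.38 = 72% of the expected count. That ratio takes an omission for granted and says nothing about its probability. It also rests on the no-dropout and background-rate assumptions above. It shows only that, with so few deaths, one missing from the table would be noticeable.

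Severity: minor.

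**What to change.** In SAP 14.1, summarize and list every fatal AE recorded or reported in the study, whatever its onset, with fatal TEAEs as a flagged subset. In the listing, show onset day, day of death and days since the last dose. If the sponsor prefers to keep the restriction to TEAEs, SAP 19 should declare it as a change from Protocol 9.5.2 and give the reason.

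The cost is one sentence in the SAP and one revised table and listing, with no new data collection. The reported number of fatal events could be slightly higher.
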